3.1 Study arm 1: HCL as control treatment and DHFCL as index treatment

A recent cross over study of the index intervention treatment (DHFCL) showed a median mean TIR of 86% (SD 4%).¹ Previous studies show a mean TIR under HCL treatment of 70 to 78% (SD 16% to 17%). ²⁻⁴ To be conservative, we assume a 7% increase in mean TIR from 78% under the HCL control treatment (SD 17%) to 85% under the index intervention treatment (SD 4%), using the two sample t-test with unequal variances, two-sided significance level of 0.05 and a power of 90%. Accordingly, the required sample size for this arm is 68 per group. To allow for potential loss to follow-up and to address the main secondary endpoints, we include a sample size of 85 per group in this arm of the trial: 85 in the HCL control treatment group and 85 in the DHFCL index treatment group.

3.2 Study arm 2: MDI+FGM/CGM as control treatment and DHFCL as index treatment.

Previous studies showed a mean TIR under MDI+FGM/CGM treatment of 50-59% (SD of 12 to 20%).⁵ To be conservative again, we assume a mean TIR in the MDI+FGM/CGM control group of 70% (SD 20%) and for the DHFCL index intervention of 85% (SD 4%) (similarly as above), thus assuming a 15% increase in mean TIR due to the index intervention. Using the two sample t-test with unequal variances, two-sided significance level of 0.05 and a power of 90%, the required sample size for this arm is 22 per group. To allow for potential loss to follow-up and to address the main secondary endpoints we include a sample size of 35 per group in this arm of the trial: 35 in the MDI+FGM/CGM control treatment group and 35 in the DHFCL index treatment group.

4. Outcome measures

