6.1 Primary endpoint

The primary endpoint (mean TIR at 12 months) will be compared between the DHFCL treatment and the two control treatments. The analysis will be performed for each of the study arms (see above) separately. To obtain this comparison, a mixed model analysis for continuous outcomes will be performed with TIR at 3, 6, 9 and 12 months (hence forward referred to as time) as dependent variable. This is a linear regression model that includes a random intercept for center of inclusion and a residual covariance matrix to correct for multiple measurements per patient. The initial analysis will be performed with a heterogeneous autoregressive matrix that assumes different variances for each measurement, a constant correlation between adjacent measurements and consistently lowering correlation when time between measurements is longer. The first analysis will include time, treatment and an interaction between time and treatment as fixed effects. In the second analysis, correction for the predefined prognostic factors, i.e. TIR at baseline, patients age and sex, will be included in the analysis as fixed effects. As the primary endpoint comparison is defined at 12 months, a specific contrast will be included in the analysis to compare mean TIR at 12 months between DHFCL control treatments. Results will be reported as difference in mean TIR with 95% confidence intervals (CIs). P-values will only be reported for the primary analysis in the ITT population. Study arm 1 and 2 will be considered two separate trials in different populations and as such no multiplicity correction is planned for performing these two primary comparisons under a single study protocol. The p-value for study arm 1 and study arm 2 will each be separately compared to the threshold 0.05 to declare significance.

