The primary analysis may result in convergence problems when the residual covariance matrix is not correctly specified, given the data. In this case, the residual covariance matrix may be adjusted. Convergence problems may also arise for the estimation of the random intercept for center of inclusion when one or more centers include a low number of patients or when included patients from different centers show very similar outcome measurements. In this case, the random intercept may be excluded from the analysis and the addition of a variable representing academic centers versus peripheral centers may be added to the analyses models as a fixed effect. The regression model with residual covariance matrix is specifically chosen as the primary analysis, as it allows to incorporate all non-missing measurements of patients over time. Further details on missing outcomes are given in section 7 on missing data.

Validity of the distributional assumptions for the main analysis model (normal distribution, homoscedasticity) will be assessed with residual analysis. Raw residuals from a covariance pattern model may (compared to a 'standard' linear regression) show both correlation and unequal variances. Raw residuals will be transformed with Cholesky decomposition prior to the assessment described in this section.¹⁸

Histograms and QQ-plots will be created to assess normality of residuals. Residuals will be plotted against raw and normalized predicted values to assess homoscedasticity and linearity. Violation of the assumption of homoscedasticity will be corrected with robust (i.e. Hubert-White's) estimation of standard errors.¹⁸

When a serious violation of the normality assumption is observed in the residual plots, the main analysis will be changed to a mixed regression analysis based on beta distributions.¹⁹ The steps for inclusion of predefined prognostic factors will be included as specified for the primary analysis (see above). Multiple measurements per patient will be corrected with a random intercept. The residual covariance matrix will be excluded from the model, as such models cannot be estimated under maximum likelihood.

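### SAP 6.1 answers likely unequal variances with plain Huber-White standard errors but fixes no block, small-sample correction or degrees of freedom; taken over centres, the 12-month test is liberal

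*SAP*

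**What the plan says.** Section 6.1 describes the primary model, fitted separately in each study arm, as one that "includes a random intercept for center of inclusion and a residual covariance matrix" for the repeated visits of a patient. The starting residual structure is a "heterogeneous autoregressive matrix that assumes different variances for each measurement". Variances may therefore differ by visit; no variance by treatment group is mentioned.

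Residuals are Cholesky-transformed and plotted. For unequal variances the rule is: "Violation of the assumption of homoscedasticity will be corrected with robust" standard errors of the Huber-White type. Nothing is said about the unit over which the sandwich is summed, a finite-sample correction or the reference distribution.

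If estimating the centre effect causes convergence problems, there is an exit: "In this case, the random intercept may be excluded from the analysis". A serious departure from normality moves the main analysis to beta regression. On the decision rule: "The p-value for study arm 1 and study arm 2 will each be separately compared to the threshold 0.05 to declare significance".

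Sections 3.1 and 3.2 plan on SDs of 17 against 4 (arm 1) and 20 against 4 (arm 2), "using the two sample t-test with unequal variances, two-sided significance level of 0.05 and a power of 90" percent.

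**The concern.** The plan expects the control group to be four to five times as variable as the DHFCL group. A covariance matrix that varies by visit but not by group cannot absorb that, and Cholesky scaling with such a matrix leaves the difference visible. If the planning SDs are roughly right, the residual plots will call for the remedy.

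The classical sandwich needs many independent blocks. With a random centre intercept, patients in one centre are correlated, so the marginal covariance is block-diagonal by centre and the sandwich sums over centres. With few centres its standard error is too small, and normal or residual degrees of freedom are far too many. On this path it would supply the p-value that is compared with 0.05. Because the choice is open, it could also be made with the results in view.

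**Working it through.** **Inputs from the SAP.** Two-sided alpha 0.05; SDs 17 and 4 with 85 per group (3.1); SDs 20 and 4 with 35 per group (3.2); 1:1 allocation stratified by centre (introduction). **Assumed:** 4 to 20 centres (K) and a between-centre SD of 2 or 3 points; the SAP gives neither.

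**1. The plan's own figures reproduce.** For the unequal-variance t-test, SE = √[(s₁² + s₂²)/n] and df = (s₁² + s₂²)²(n − 1)/(s₁⁴ + s₂⁴).
- Arm 1, n = 68: SE = √(305/68) = 2.118, df = 74.4, 7/2.118 = 3.31, power 0.904.
- Arm 2, n = 22: SE = √(416/22) = 4.348, df = 22.7, 15/4.348 = 3.45, power 0.910.

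The stated 68 and 22 are right. At the enrolled 85 and 35 per group, power is 0.955 and 0.989.

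**2. Equal group sizes already protect the model-based SE.** With n per group the pooled-variance SE is √[2 × (s₁² + s₂²)/2 / n] = √[(s₁² + s₂²)/n], the same as the unequal-variance SE. Only the degrees of freedom differ.

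**3. Closed form for the centre-block sandwich.** Take K equal centres, each 1:1, with within-centre differences d₁…d_K. The centre effect cancels in each d and the estimate is their mean. The uncorrected sandwich variance is Σ(d_k − d̄)²/K², which is (K − 1)/K times the unbiased Σ(d_k − d̄)²/[K(K − 1)]. Testing against 1.96 therefore rejects when |t on K − 1 df| > 1.96 × √[(K − 1)/K]. The group SDs drop out, so both study arms should show about the same error.

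**4. Null simulation of the 12-month contrast.** Group SDs from the SAP, centre SD 3, centre intercept by REML, equal centres, residual df, 4,000 runs per setting:

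| Centres K | Threshold on t(K−1) | Closed form | Arm 1 | Arm 2 | Mean SE / true SE, arm 1 |
|---|---|---|---|---|---|
| 4 | 1.697 | 0.1882 | 0.191 | 0.175 | 0.79 |
| 6 | 1.789 | 0.1336 | 0.132 | 0.123 | 0.87 |
| 8 | 1.833 | 0.1094 | 0.107 | 0.109 | 0.90 |
| 10 | 1.859 | 0.0959 | 0.102 | 0.096 | 0.91 |
| 14 | 1.889 | 0.0815 | 0.072 | 0.076 | 0.96 |
| 20 | 1.910 | 0.0713 | 0.069 | 0.066 | 0.97 |

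Monte Carlo error is about 0.003-0.006. Unequal centre sizes raise the error somewhat: at K = 8, 0.112 (arm 1) and 0.124 (arm 2); at K = 14, 0.092 and 0.094.

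**5. Other settings agree in direction.** All use centre SD 2.
- Adjusted for baseline, age and sex: arm 2 gives 19% (5 centres), 12% (10), 10% (14) and 9% (20); arm 1 gives 18%, 10%, 9% and 7.5%.
- Four visits with dropout, within-patient correlation 0.7 (assumed): arm 2 gives 16% (5), 11% (8), 10% (10) and 8% (14); arm 1 gives 14% (5), 10% (10) and 9% (14).
- A further 12-month run: 15% (5), about 10% (10), 8% (14) and 6-7% (20) in both arms.

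**6. Alternatives, centre SD 3 unless stated.**
- Model-based SE: 0.045-0.063.
- Patient-block sandwich, residual df: 0.051-0.064 in arm 1, 0.056-0.068 in arm 2.
- Uncorrected centre sandwich, t on K − 1 df: 0.049-0.077.
- Centre sandwich with K/(K − 1) correction and t on K − 1 df: 0.044-0.058 (equal centres), 0.057-0.066 (unequal); 4.9-5.6% in the four-visit setting with centre SD 2.

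**The case against.** A reader might infer that the plan prescribes an uncorrected centre-level sandwich, and so makes the confirmatory interval too narrow. The SAP does not say that. Blocks, correction and reference distribution are all unstated, and section 6.4 leaves the software as SAS or R, so no default is fixed either. Section 6.1 ties the residual matrix to repeated measurements within a patient and speaks of a covariance pattern model. Patient blocks are therefore a possible reading, and on that reading the error is only 5-7%. This stands, and it limits the point to an open rule with a liberal plain reading.

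The size also depends on a number that the SAP does not give: nearly fourfold at 4 centres, modest at 20. That stands too. Much of the excess comes from the reference distribution, since K − 1 df alone brings it down to 0.049-0.077. This is a reason to state the degrees of freedom.

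Nor is this path certain to yield the p-value. The centre intercept may be dropped, and a centre SD of 2 implies an intraclass correlation of only 4/(4 + 152.5) = 2.6% in arm 1 and 4/(4 + 208) = 1.9% in arm 2. Unequal SDs also thicken the pooled tails: kurtosis is 3 × [(17⁴ + 4⁴)/2] / 152.5² = 5.4 in arm 1 and, likewise, 5.6 in arm 2. Normality might then be judged seriously violated and beta regression used. These exits make the sandwich a likely path, not the only one. They do not repair the rule where it applies: the intercept is dropped for convergence problems, not because robust standard errors are chosen.

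Finally, one might infer that the smaller arm is much the worse off. With centre blocks the error follows the number of centres, and the two arms behave alike at the same K. Only the patient-block version is slightly worse in arm 2.

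**Conclusion.** The point holds as a badly fixed rule for the confirmatory standard error. The plan's own SDs make its trigger likely. On its plain reading the remedy replaces a model-based test that is already near nominal (about 4.5-6%) by one with a type I error of about 15-19% at 4-5 centres, about 10% at 10 and about 6-9% at 20. With patient blocks the error stays at about 5-7%.

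This rests on an assumed number of centres, an assumed centre SD of 2-3 points, the planning SDs and 1:1 allocation within centre. Most runs used the 12-month visit with complete data; the four-visit runs with dropout agree. The documents do not establish which version would be used, so a type I error well above 5% is a risk that the rule leaves open, not a property of the plan.

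**What to change.** Replace the rule in 6.1:

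- Handle between-group heteroscedasticity with a prespecified residual covariance specific to treatment group, with Satterthwaite or Kenward-Roger degrees of freedom.
- If a sandwich SE is used instead, apply a small-sample correction (CR2 or MBN type) and degrees of freedom matched to its blocks: Satterthwaite, or K − 1 for centre blocks.
- Use patient blocks only when the centre random intercept has been dropped or replaced by fixed effects. Treating patients as independent fits badly with a model that keeps a centre effect.

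The simulations cover the K/(K − 1) correction with K − 1 df. They do not cover CR2, MBN or the group-specific covariance, so the chosen version should be checked once by simulation with the actual number and sizes of centres. The cost is a few sentences in the SAP, a little more programming and slightly wider confidence intervals.

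### The beta mixed model that replaces the primary analysis after non-normal residuals has no treatment-specific dispersion stated; fitted in its ordinary form at the planned SDs, it biases the 12-month TIR difference itself.

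*SAP*

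**What the plan says.** Section 6.1 of the SAP defines the primary analysis, run separately in study arm 1 (DHFCL against HCL) and study arm 2 (DHFCL against MDI). It is a linear model for TIR at 3, 6, 9 and 12 months with a 12-month contrast, tested at 0.05 in each arm. Its residual covariance is a "heterogeneous autoregressive matrix that assumes different variances for each measurement"; variances differ by visit, and no difference by treatment is mentioned. The effect measure is the difference in mean TIR with a 95% CI.

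The same section then sets the model checks:

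- Before the plots are read: "Raw residuals will be transformed with Cholesky decomposition prior to the assessment described in this section".
- Unequal variance: "Violation of the assumption of homoscedasticity will be corrected with robust" standard errors.
- Serious non-normality, judged by eye with no cut-off: "the main analysis will be changed to a mixed regression analysis based on beta distributions".
- In that beta model: "Multiple measurements per patient will be corrected with a random intercept", and "The residual covariance matrix will be excluded from the model, as such models cannot be estimated under maximum likelihood".

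The section does not mention the precision parameter of the beta model, whether precision or random-intercept variance may differ by treatment, or how the fit is turned into a difference in mean TIR.

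Sections 3.1 and 3.2 assume means of 78% (SD 17%) against 85% (SD 4%) in arm 1 and 70% (SD 20%) against 85% (SD 4%) in arm 2. Both arms are sized with an unequal-variance t-test.

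**The concern.** The beta model is not a sensitivity analysis. Once triggered, it becomes the confirmatory test. In a linear model, unequal spread between groups affects only the standard error, and the SAP already deals with that. In a beta model the mean and the precision are estimated jointly, so a precision that is wrong for each group also moves the estimated means. A robust standard error around a shifted estimate does not bring the estimate back.

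The sample size section expects the situation in which this matters. Unequal spread also makes the switch more plausible. If residuals from a wide and a narrow group are scaled with one covariance matrix, the pooled residuals look heavy-tailed. At stake are the size of the primary estimate in both arms, the power of arm 1, and in arm 1 the risk of a false conclusion in favour of control.

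**Working it through.** **Inputs.** Means, SDs, alpha and power come from sections 3.1 and 3.2; group sizes of 85 and 35 and the four visits from the SAP introduction and section 6.1. Assumed, because the SAP gives no value: within-patient correlation 0.6 (0.3 to 0.85 also tried), beta-shaped data unless stated, and complete follow-up.

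**The plan's own figures.** Welch t-test, noncentrality = difference / √[(SD₁² + SD₂²)/n]:

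- Arm 1, n = 68: 7/√(305/68) = 3.31, power 90.4%. At n = 85, 95.5%.
- Arm 2, n = 22: 15/√(416/22) = 3.45, power 91.0%. At n = 35, 98.9%.

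The stated 68 and 22 reproduce and are not in question.

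**Spread that a single dispersion can represent.** Beta precision = μ(1−μ)/SD² − 1:

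- HCL: 0.1716/0.0289 − 1 = 4.9
- MDI: 0.21/0.04 − 1 = 4.25
- DHFCL: 0.1275/0.0016 − 1 = 78.7

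DHFCL precision is therefore 16 to 19 times that of control. The planned variance ratios are 17²/4² = 18.1 and 20²/4² = 25. With one precision, the implied ratio is that of μ(1−μ): 1.35 in arm 1 and 1.65 in arm 2. Through a common logit-scale random intercept it is the square of that, 1.81 and 2.71.

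**Large-sample limit, 12-month data only, one precision.**

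| Scenario | True difference | Fitted control mean | Fitted DHFCL mean | Fitted difference |
|---|---|---|---|---|
| Arm 1 | 7 | 80.5 | 81.9 | 1.3 |
| Arm 2 | 15 | 72.2 | 81.3 | 9.1 |
| Arm 1, both means 78 | 0 | 80.6 | 75.4 | −5.2 |

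With logit-normal data the first two fitted differences are 2.5 and 10.0. The bias is zero at a DHFCL SD of 14.65% in arm 1 (about 14% by interpolation of the four-visit results) and about 15.6% in arm 2. At 17% against 17% in arm 1 the limit is 9.2, an overstatement.

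**Four visits, random intercept, one precision, one random-intercept variance** (1000 simulated trials, correlation 0.6, difference averaged over the random intercept):

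| | Arm 1 | Arm 2 |
|---|---|---|
| True difference | 7 | 15 |
| Mean estimate | 3.0 | 11.1 |
| 95% CI coverage | 39% | 71% |
| Power | 38% (34% with robust SEs) | 92% |
| Analytic Welch power | 95.5% | 98.9% |
| Rejection with equal means | 55%, nearly all toward control | 19% |

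With equal means the arm 1 estimate averages −3.9. With complete data the 12-month contrast of the linear model equals the raw mean difference, so Welch stands in for the SAP's linear model with robust errors. A separate large-sample fit at correlations 0.3 to 0.85 gave 2.0 to 3.2 points in arm 1 and 10.3 to 11.4 in arm 2.

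**Sensitivity, arm 1 power with a single dispersion.**

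- Correlation 0.4 / 0.8: 42% / 55%.
- Adjusted for baseline TIR: 54%.
- DHFCL SD 8%: 57% (estimate 4.1). SD 12%: 82% (estimate 5.9).
- If 10% / 20% of DHFCL patients have control-type outcomes (assumed; section 7.3.2 keeps patients who stop DHFCL in the ITT analysis): 33% / 26%, against 90% / 79% for Welch. The overall DHFCL SD is then about 6.9% / 8.9%.
- Logit-normal data at SD 4%: 58% (63% at correlation 0.8), with false rejection 48%.

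**Group-specific dispersion.** Freeing precision alone is not enough: arm 1 still gives 5.6 and 4.0 points at correlations 0.7 and 0.85. Freeing precision and random-intercept variance gives 7.1 in arm 1 (power 99%, false rejection 5.8%) and 15.0 in arm 2 (100%, 6.4%). The difference must be averaged over the random intercept; read at an intercept of zero, the same type of fit gives only 3.1 to 6.2 points in arm 1.

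**Trigger.** Kurtosis of an equal mixture of two normals with variance ratio r is 3·[(1+r²)/2]/[(1+r)/2]². With r = 18.06 it is 5.4, and with r = 25 it is 5.6, against 3 for a normal. On the simulated beta data, scaling within group lowers kurtosis from 6.3 to 3.3 (arm 1) and from 5.3 to 2.9 (arm 2). Skewness of −0.5 and −0.4 remains, and with 10% reversion the within-group kurtosis is 6.9 and 4.8.

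**The case against.** The SAP never says that one precision will be used. An analyst could fit group-specific dispersion and still comply. The single-dispersion form is an assumption about common practice, so this is an under-specified contingency and not a stated error. That stands. It does not remove the point: the choice moves the primary estimate by about 4 points and, as written, could be made after the data are seen.

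Unequal variance has its own rule (robust standard errors) and only non-normality triggers the switch; on that primary route the analysis works. That also stands. But residuals scaled with one covariance for both groups can make unequal variance look like non-normality. How often the switch would occur is not known, so none of the error rates above is an operating characteristic of the SAP as a whole.

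The planned DHFCL SD of 4% comes from one crossover study and may not describe 12-month ITT data. This is correct, and the bias shrinks as that SD rises.

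A reader might infer that arm 1 would probably miss a true 7-point benefit. The documents do not support that as a general statement: power under the flaw runs from about 26% to 82% across the settings examined. Nor is a bias toward control inevitable, since the direction depends on the observed SDs and means.

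Keeping the linear model with robust errors as primary and using the beta model as a sensitivity analysis would also avoid the problem. That is a legitimate alternative.

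**Conclusion.** The point holds as a conditional one and should be fixed. It rests on two conditions: the residual plots lead to the switch, and one precision with one random-intercept variance is fitted.

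If both hold with SDs like those planned, the estimated difference is understated by about 4 points in each arm. Arm 1 loses substantial power: about 26% to 57% in most settings with an SD of 4-8% among patients who stay on DHFCL, and more at larger SDs. With equal means it is biased toward control. Arm 2 mainly reports too small an effect. Its power stays at about 92% in the base case and falls to 83% / 70% under the assumed 10% / 20% reversion (Welch 96% / 85%).

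Correlation, data shape and reversion are assumptions. Age, sex, centre and drop-out were not simulated. Confidence is medium, because neither the trigger nor the eventual dispersion structure can be known from the SAP.

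**What to change.** In section 6.1:

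1. State that, if the beta model is used, precision and random-intercept variance are both estimated by treatment group. The reported effect is the marginal 12-month difference in mean TIR (averaged over the random intercept and standardised over covariates) with its 95% CI.
2. Judge normality on residuals scaled within treatment group. State that unequal group variance alone leads to robust standard errors in the linear model and not to the beta model. This lowers the chance of an unneeded switch but does not exclude it, so item 1 is still needed.
3. Optionally, allow a group-specific residual covariance in the linear model. The planned robust standard errors already protect that model.

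The cost is a few sentences and a few extra dispersion parameters, with no extra patients or data. The downside is slightly less stable estimation in arm 2, with 35 per group (simulated false rejection about 6%).
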